#### **6.2** DATA ELEMENTS

## 6.2.1 Human Data Sharing Plan

- Documentation of dosage and timing of drug administration
- Outside laboratory, radiologic, and pathology results will be sent to the PI and entered into NCI C3D at NIH
- NIH labs and tests will be downloaded into C3D

Version Date: 04/16/2025

• A pre-existing (baseline) laboratory abnormality will be considered the last one obtained prior to the first dose of drug, unless the PI considers an abnormality of higher grade occurring within 100 days prior to the first dose to be a truer baseline.

## 6.3 DATA SHARING PLANS

# 6.3.1 Human Data Sharing Plan

#### What data will be shared?

Human data generated in this research will be shared for future research as follows:

- Coded, linked data in an NIH-funded or approved public repository.
- Coded, linked data in BTRIS (automatic for activities in the Clinical Center)
- Identified or coded, linked with approved outside collaborators under appropriate agreements.

#### How and where will the data be shared?

Data will be shared through:

- An NIH-funded or approved public repository: clinicaltrials.gov, and dbGaP
- BTRIS (automatic for activities in the Clinical Center)
- Approved outside collaborators under appropriate individual agreements.
- Publication and/or public presentations.

#### When will the data be shared?

- Before publication.
- At the time of publication or shortly thereafter.

## 6.3.2 Genomic Data Sharing Plan

Unlinked genomic data will be deposited in public genomic databases such as dbGaP in compliance with the NIH Genomic Data Sharing Policy.

#### 6.4 RESPONSE CRITERIA

## 6.4.1 Rules for response assessment

- No G-CSF or GM-CSF at least 4 weeks before major response (i.e. partial response or complete response).
- No transfusions at least 4 weeks before major response.
- Hgb requirement for major response may be dropped if iron stores (ferritin or iron saturation) are low

## 6.4.2 Complete remission (CR)

All of the following:

- Absolute neutrophil count (ANC)  $\geq 1500/\text{mm}^3$
- Platelets  $\geq 100,000/\text{mm}^3$

Version Date: 04/16/2025

- Hgb  $\geq$  11 g/dL
- Regression of splenomegaly on physical exam or by imaging studies.
- Lymph nodes  $\leq 2$  cm by short axis, unless larger lymph nodes not due to HCL
- Absence of hairy cells on BM aspirate smears and H/E stain of the BM biopsy negative for HCL. If the negative BM is before 4 weeks off of growth factors or transfusions, the CR will begin after the 4 week time point once the normal blood counts are consistent with CR.
- CR with MRD in the BMBx by IHC is defined as CR and a ratio of CD20+ cells to T cells of at least 1, and most of the CD20+ cells consistent with HCL.
- CR with MRD in the peripheral blood is defined as CR and a positive peripheral blood FACS or PCR. Suspicious flow is considered positive per protocol.
- Participants meeting all criteria for CR except minimum levels of ANC, platelets and Hgb will be considered CR if MRD is absent by BMBx IHC and by flow cytometry of blood and bone marrow.

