Long-term follow-up of these 28 patients, including 12 who received the upper dose 50 mcg/kg every other day for 3 doses (QODx3), and an extension cohort of 21 patients receiving this dose, documented a CR rate of 64% in the 33 patients receiving 50 mcg/kg QODx3. Moreover, of 32 patients evaluated for minimal residual disease (MRD) with bone marrow biopsy (BMBx) immunohistochemistry (IHC) and flow cytometry of blood and bone marrow aspirate (BMA), 11 (34%) were MRD-negative. Median CR duration was not reached (up to 72 months) in those MRD-negative vs 13.5 months in those MRD+ (p<0.0001). Of the 3 tests for MRD, the most sensitive by far was BMA flow cytometry, and patients MRD+ by this study were sometimes positive by blood flow cytometry, IHC, or both [9]. Multicolor high sensitivity flow cytometry was used for both blood and BMA, and results read as suspicious are considered negative. MRD+ by IHC of BMBx requires at least as many B as T-cells, and for most of the B-cells to be consistent with HCL [10]. As exploratory endpoints, MRD is also determined by PCR, using consensus primers to a variable framework domain (FR1, FR2 or FR3), and a junctional or constant domain (JH or CH) of the immunoglobulin heavy chain rearrangement (IgH) [11, 12]. This assay, performed in the Molecular Pathology Section of the Laboratory of Pathology, NCI, is considered positive if the band corresponding to the HCL IgH can be recognized over a background of IgH bands from normal B-cells. Lack of normal B-cells, either due to HCL, chemotherapy or rituximab, may allow the HCL IgH band to more easily be seen. A research PCR assay is also done in the [name] Lab using patient- specific primers with a probe [11]. This patient- or clone-specific assay can detect 1 HCL in 10^6 normal cells but requires a different PCR assay for each patient.

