## 2.4.1 Within 6 months before drug

- MRI Cervical and Thoracic (C- and T-) Spine to correlate the status of the BMBx with the vertebral bone marrow aspiration (BMA) signal by MRI. May be cancelled at the discretion of the PI, including if participant unable to get MRI at NIH and not covered by insurance outside NIH.
- CT Neck-pelvis or MRI
- Abdominal Ultrasound (U/S) will be done to exclude lymph nodes potentially impacting the biliary tree
- Echo, PFTs, stress test
- BMA for FACS and PCR (if evaluable). Blood PCR should be done at the same time as BMA PCR in the CLIA certified laboratory at the Laboratory of Pathology, CCR/NCI. HLA test (May be done any time before initiation of study therapy)

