- To be done at bone marrow time points, to correlate the status of the BMBx with the vertebral BMA signal by MRI. May be cancelled at the discretion of the PI, including if participant unable to get MRI at NIH and not covered by insurance outside NIH.
- 15. This test will be conducted within 3 days prior to enrollment
- 16. Performed within 4 weeks before initiation of study therapy.
- Adverse events and concomitant medications will be monitored continuously in every visit.
- 18. Samples collected during the course of this study will be stored, tracked, and disposed of as specified in investigator's companion protocol, 10C0066, on which all participants will be co-enrolled.
- During the moxetumomab pasudotox-tdfk infusion, vital signs will be obtained every 15 (±10) minutes, then every hour (±30 minutes) for an additional 4 hours during Cycle 1. During subsequent cycles, vital signs will be obtained every 15 (±5) minutes during the moxetumomab pasudotox-tdfk infusion, then every hour (±30 minutes) for an additional 2 hours. Vital signs will also be obtained on Day 8 ± 1 day for the first 3 dosing cycles.
-  May be done up to 3 days prior to day 1 of cycle.
- Must be done on day 1 of cycle 1 prior to treatment.
- 22. Cycle interval may be shortened to 25-27 days due to logistical reasons.
-  Pre-cycle tests may be done 0 to 2 days before and maybe combined with either baseline for cycle 1 or day 1 or both.
- 24. During rituximab/Ruxience infusion on cycle 1 day -2 vital signs will be obtained with every dose change and as needed.
- 25. Must be completed on day 8 but may be cancelled at PI discretion.
- 26. Pre-cycle and pretreatment on days 3, 5, and 8.
- 27. Pre-cycle bone marrow and scans to be done at the discretion of the PI based on the participants HR status.
- 28. Sampling pre-dose before cycles 1,2,3,5, and 7.
- 29. Sampling at 3 and 6 months after the end of treatment evaluation.
- 30. Sampling in case HUS or CLS are observed.
- 31. Cycle 1 IFE to be done pre cycle may be combined with baseline labs +/- 1-4 days and again pre moxetumomab pasudotox-tdfk on Cycle 1 day1.
- 32. Screening labs can be combined with pre cycle 1 labs if done within 5 days of day -2 with the exception of the labs listed as day -2 labs

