• Sample size determination for amendment dated 9/21/2021: As of July 2021, a total of 12 participants were enrolled without DLT up to that point, making it likely that 3 participants will be enrolled with moxetumomab pasudotox-tdfk 30 mcg/kg and rituximab 375 mg/m², and 10 with moxetumomab pasudotox-tdfk 40 mcg/kg and rituximab 375 mg/m². Of the first 9 participants so far evaluated for response, 7 (78%) achieved CR, all MRD-free.

Given the encouraging safety and efficacy data from the phase 1 trial, it is desirable to increase the number of participants to gain more experience with moxetumomab pasudotox-tdfkand rituximab and be able to determine whether the efficacy of the combination at 30-40 mcg/kg of moxetumomab pasudotox-tdfk is better than our historical experience of 40-50 mcg/kg of moxetumomab pasudotox-tdfk alone tested for MRD at NIH. Historically, 30 of 64 evaluable phase 1-3 participants treated with moxetumomab pasudotox-tdfk alone achieved MRD-free CR assessed by bone marrow aspirate flow.

To enable additional participants to be enrolled affordably, starting with participant 14, participants will receive the biosimilar Ruxience instead of rituximab. Moxe-R thus represents the combination of moxetumomab pasudotox-tdfk with either rituximab or Ruxience.

If we are being conservative, the 7 of 9 participants who achieved MRD-free CR to date on Moxe-R would need to be considered an interim evaluation and its successful result would be the basis for deciding to add more participants. As such, it would be statistically appropriate to aim for a 0.025 one-sided test between 30/64 and the participants on the current trial. With a total of 26 evaluable participants on Moxe-R and 64 prior participants, a Fisher's exact test with a one sided 2.5% significance level will have 79.8% power to detect a difference between 80% MRD-free CR rate on the present trial and 47% from the 30/64 participants in the prior trials.

While a total of 26 evaluable participants will be enrolled, the accrual ceiling will be set at 30 to include screen failures and inevaluable participants.

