## 10.4.3 Analysis of the Secondary Endpoint(s)

- Response rates, MRD-free rates, and response durations will be reported descriptively, and the latter will be determined using Kaplan Meier Analyses.
- The MRD-free CR rates will be compared between evaluable participants on this trial and the 30 of 64 evaluable phase 1-3 participants who achieved MRD-free CR from moxetumomab pasudotox-tdfk using a Fisher's exact test, taking the interim results from this trial into consideration.
- The change from rituximab to Ruxience is not expected to result in a change to the CD20 Mab, and the comparison between participants 1-13 treated with moxetumomab pasudotox-tdfk rituximab and participants 14-26 treated with moxetumomab pasudotox-tdfk Ruxience will have limited power to detect a difference between rituximab and Ruxience in HCL. After enrollment of 26 participants, if the difference in MRD-free CR rate from moxetumomab pasudotox-tdfk rituximab vs moxetumomab pasudotox-tdfk Ruxience results is p>0.30 or higher, the results from the 2 groups will be considered close enough to be pooled and the full 26 participants could be compared against the 64 from the moxetumomab pasudotox-tdfk monotherapy studies.

Version Date: 04/16/2025

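### A positive blood PCR alone makes a CR MRD-positive, yet blood PCR is optional from end of treatment onward, so the tested MRD-free CR rate can depend on whether the test was done

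*Combined protocol and SAP*

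**What the plan says.** **Definition.** Section 6.4.2 holds the trial's only rule for residual disease in blood: "CR with MRD in the peripheral blood is defined as CR and a positive peripheral blood FACS or PCR". Either test suffices. A separate bullet in 6.4.2 covers participants who meet every CR criterion except blood counts. They are "considered CR if MRD is absent by BMBx IHC and by flow cytometry of blood and bone marrow", with no mention of PCR.

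**Schedule.** In the Study Calendar (3.4), the blood PCR row is marked at baseline and pre-cycle with no qualifying footnote. At EOT, EOT+6 months and restaging it carries footnote 38, which makes it optional. It is not scheduled at the F/U visits. The marrow row (biopsy, and aspirate with flow and PCR) is marked at EOT without an optional footnote. During treatment, footnote 27 applies: "Pre-cycle bone marrow and scans to be done at the discretion of the PI".

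**Role of PCR.** Section 1.2.1 says: "As exploratory endpoints, MRD is also determined by PCR".

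**Analysis.** Section 10.4.3 compares the MRD-free CR rate with the 30 of 64 earlier "participants who achieved MRD-free CR from moxetumomab pasudotox-tdfk using a Fisher's exact test". The same section says: "Response rates, MRD-free rates, and response durations will be reported descriptively". The MRD-free CR rate also decides, at p>0.30, whether the rituximab and Ruxience groups are pooled. Section 10.2 describes the historical participants as having "achieved MRD-free CR assessed by bone marrow aspirate flow".

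**The concern.** Take two participants in CR at EOT with identical negative flow and IHC. One has no blood PCR and nothing in 6.4.2 makes that CR MRD-positive. The other has a positive blood PCR and is CR with MRD. No section says how to classify a CR with no blood PCR. The effect runs one way: leaving the test out can never lower the MRD-free rate.

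PCR-only positives are plausible on the protocol's own account. Section 1.2.1 notes that depletion of normal B-cells, including by rituximab, can make the leukemic band easier to see, and that the clone-specific assay can detect one HCL cell in a million. Section 6.4.2 does not say which PCR assay counts.

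At stake are the comparison with 30/64 and the pooling check before it. Counting blood PCR here would also score this trial by a test not named for the comparator, and only in those who happened to have it.

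**Working it through.** **Inputs.** From 10.2: 26 evaluable participants against 64 historical; assumed rates 80% and 47%; one-sided Fisher's exact test at 0.025; stated power 79.8%. From 10.2 and 10.4.3: observed comparator 30/64.

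**1. Reproduce the planned power.** Sum Binomial(26, 0.80) × Binomial(64, 0.47) over all 2×2 tables whose one-sided hypergeometric p is at most 0.025. Result: 0.798, matching the stated 79.8%.

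**2. Success boundary against the observed 30/64.** One-sided Fisher p-values:

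| MRD-free CR | p |
|---|---|
| 18/26 | 0.0442 |
| 19/26 | 0.0202 |
| 20/26 | 0.0081 |
| 21/26 | 0.0028 |

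Success needs 19/26. Reclassifications that reverse it by bringing the count to 18: 19−18 = 1, 20−18 = 2, 21−18 = 3. The planned 80% rate corresponds to 0.80 × 26 = 20.8, about 21 participants, so three PCR-only positives would turn the expected result into a failure.

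**3. Power under assumed PCR-only positivity.** Let q be the share of flow- and IHC-negative CRs that are blood-PCR positive, and t the share tested. The MRD-free rate is then 0.80 × (1 − t·q). The documents do not give q, so the values below are assumptions. Power is calculated as in step 1.

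| q | MRD-free rate, all tested | t=0 | t=25% | t=50% | t=75% | t=100% |
|---|---|---|---|---|---|---|
| 5% | 76% | 79.8% | 76.6% | 73.3% | 69.8% | 66.1% |
| 10% | 72% | 79.8% | 73.3% | 66.1% | 58.6% | 51.0% |
| 20% | 64% | 79.8% | 66.1% | 51.0% | 36.5% | 24.1% |

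**4. Pooling check.** Section 10.4.3 names no test for the p>0.30 rule. Assuming a two-sided Fisher test with 13 per group, 11/13 against 8/13 gives p=0.38 (pool) and 11/13 against 7/13 gives p=0.20 (do not pool). One reclassification can change that decision too.

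**5. Which assessments are affected.** An MRD-free CR documented before a cycle falls where blood PCR is scheduled without the optional mark. The gap therefore concerns status set or revised at EOT or later. CR requires a negative marrow, and pre-cycle marrow is discretionary, so EOT may often be the deciding assessment. The documents do not say how often.

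**The case against.** The strongest reply is that PCR was never meant to count. Section 1.2.1 calls it exploratory, the incomplete-counts rule uses only IHC and flow, and the comparator was scored by marrow aspirate flow. Neither 6.4.2 nor 10.4.3 expressly defines MRD-free CR for the Fisher test. On that reading optional PCR has no effect on the tested endpoint. This is reasonable as intent, but the text does not say it. Section 1.2.1 is background and conflicts with 6.4.2 elsewhere: suspicious flow is read as negative in 1.2.1 and as positive in 6.4.2. It cannot be taken to override the response criteria.

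It also stands that q is unknown, that the comparison of nobody tested with everybody tested is an extreme, and that this is a secondary endpoint in a trial whose primary question is safety.

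A reader might make three further inferences, which the documents do not support:

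- That the optional PCR alters how many cycles are given. The rule on cycles after CR without MRD operates between cycles, where blood PCR carries no optional mark. A test at EOT or later comes after treatment has ended.
- That 2.4.1 requires blood PCR alongside marrow PCR at EOT. Its statement, "Blood PCR should be done at the same time as BMA PCR", sits under the pre-treatment baseline evaluation and does not contradict footnote 38.
- That uptake did differ by arm or over time, or that tests were withheld. Nothing in the documents shows this.

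**Conclusion.** The concern holds for MRD status set or revised at EOT or later. Followed as written, 6.4.2 and footnote 38 let the only efficacy endpoint tested against historical control, and the pooling check, depend on whether an optional test was done, with any error favoring a higher MRD-free rate.

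The boundary results (19/26 succeeds, 18/26 does not, and one to three reclassifications are enough) need no assumption about PCR, only the planned 26 evaluable participants and 30/64. The power figures of 66%, 51% and 24% rest on assumed PCR-only shares of 5%, 10% and 20% with everyone tested. They show sensitivity and are not a forecast. What is established is that the plan's passages on PCR conflict and the tested endpoint has no rule for a missing PCR; it is not established that the result will turn on PCR.

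**What to change.** In 10.4.3, define MRD-free CR for both the Fisher test and the rituximab-Ruxience pooling comparison on the flow and IHC tests scheduled for everyone at EOT, excluding PCR. Name marrow aspirate flow alone as the version matched to 30/64. Report blood and marrow PCR as exploratory, giving the number tested and the number positive by arm. Score participants 1-13 by the same rule and state which rule they were scored by before.

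Confine the change to the analysis definition. On the use of MRD status in deciding cycles, the sponsor should reconcile 1.2.1, 3.1, 3.4 (with footnote 38) and 6.4.2; this review proposes no rule there.

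Requiring a blood PCR before anyone can be called MRD-free is not a good alternative. Section 2.4.1 provides for PCR only if evaluable, and the clone-specific assay has to be built for each patient. Participants without an evaluable PCR could never count as MRD-free, which would bias the rate downward.

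Cost: a few sentences in 10.4.3, a possible re-score of participants 1-13, and no new procedure. The downside is that the tested endpoint ignores residual disease seen only by PCR, which would still be reported.

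### The MRD rules written for this trial do not match the assay behind the historical 30/64, and no assay is named for the trial's own numerator, so the two groups can be scored differently

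*Combined protocol and SAP*

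**What the plan says.** **Historical side.** Section 10.2 says the 30 of 64 monotherapy patients "achieved MRD-free CR assessed by bone marrow aspirate flow". Section 1.2.1 gives the same assay for the same count. The phase 1 account in section 1.2.1 adds three points:

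- On sensitivity: "Of the 3 tests for MRD, the most sensitive by far was BMA flow cytometry".
- On equivocal flow: "results read as suspicious are considered negative".
- On PCR: "As exploratory endpoints, MRD is also determined by PCR".

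**Trial side.** Section 6.4.2 gives two definitions of CR with MRD. One is by IHC on the marrow biopsy. The other is by blood: "CR and a positive peripheral blood FACS or PCR. Suspicious flow is considered positive per protocol". Neither uses marrow-aspirate flow. That test appears only in the last bullet, which lets a participant who misses the blood-count thresholds count as CR if MRD is absent by biopsy IHC and by flow of blood and marrow.

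**The comparison.** Section 10.2 plans a "Fisher's exact test with a one sided 2.5% significance level" with "79.8% power to detect a difference between 80% MRD-free CR rate on the present trial" and "47% from the 30/64 participants in the prior trials". Section 10.4.3 repeats the comparison. Neither section names the assay for the 26 or says the 64 will be re-scored.

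**The concern.** A comparison with a fixed historical count is interpretable only if a success means the same thing in both groups. Followed as written, section 6.4.2 differs from the historical scoring in four ways, and they do not all push in the same direction.

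| Difference | Effect on this trial's rate |
|---|---|
| Suspicious flow counted as positive | lowers it |
| Positive blood PCR counted as MRD | lowers it |
| Aspirate flow, the most sensitive test, absent from the MRD bullets | raises it |
| Blood-count waiver, if the 64 did not have it | raises it |

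PCR deserves particular care. Section 1.2.1 notes that a lack of normal B-cells, including from rituximab, may make the leukaemic band easier to see on the consensus-primer assay. Counting PCR on the combination side alone could therefore act differentially. Blood PCR is also optional at end of treatment, six months later and at restaging (section 3.4, note 38), so not every participant would be exposed to that rule.

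At stake is the one efficacy comparison that the increase to 26 participants was powered for. If the scoring rule is left open in an unblinded, non-randomised comparison, it can be settled after the results are known.

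**Working it through.** **Inputs.** From section 10.2: one-sided Fisher's exact test at 0.025; 26 against 64; assumed rates 80% and 47%; historical count 30/64. From section 1.2.1: phase 1 CR rate regardless of MRD, 64% of 33. The share of participants whose status changes under section 6.4.2 is not in the documents, so the shifts below are assumed ranges.

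**Step 1: reproduce the plan's figure.** Power = Σ over x and y of Bin(x; 26, p₁) × Bin(y; 64, p₀), taken over all pairs with one-sided Fisher p ≤ 0.025. With p₁ = 0.80 and p₀ = 0.47 this gives 79.8%, as stated. With p₁ = p₀ = 0.47 the actual one-sided error is 1.5%. The arithmetic is sound, but it assumes both groups are scored alike.

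**Step 2: the cut-off against 30/64.**

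| Trial result | Rate | One-sided p |
|---|---|---|
| 18/26 | 69.2% | 0.0442 |
| 19/26 | 73.1% | 0.0202 |
| 21/26 | 80.8% | 0.0028 |

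At the boundary, one reclassified participant reverses the result. The planned result is 0.80 × 26 = 20.8, about 21; three reclassified participants bring it to 18, which fails.

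**Step 3: stricter scoring of the trial.** If a fraction f of true MRD-free CRs is re-labelled as MRD-positive, the scored rate is 0.80 × (1 − f).

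| f (assumed) | Scored rate | Power |
|---|---|---|
| 0 | 80% | 79.8% |
| 5% | 76% | 66.1% |
| 10% | 72% | 51.0% |
| 15% | 68% | 36.5% |

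**Step 4: looser scoring of the trial, with no drug effect.** The true rate is 47% in both groups, and scoring lifts the trial's rate only.

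| Scored trial rate (assumed) | One-sided error |
|---|---|
| 47% | 1.5% |
| 50% | 2.8% |
| 55% | 6.9% |
| 60% | 14.7% |
| 64% | 24.1% |

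The last row is an upper bound, because 64% is the phase 1 CR rate whether or not MRD was present. Under no effect about 0.47 × 26 ≈ 12 participants succeed, so seven would have to move to reach 19. A failure caused by scoring is therefore easier to produce than a success.

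**Step 5: re-scoring the historical group.** If the count moved from 30 to 26, 31 or 34 of 64, the cut-off would become 18, 20 or 21 of 26.

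**The case against.** The strongest reply is that this is an ambiguity in the text and not a demonstrated comparison of two endpoints. The protocol never defines MRD-free CR outright, and section 6.4.2 does not say its two MRD bullets are exhaustive. Its only statement of when MRD is absent, in the count waiver, requires negative IHC and negative flow of both blood and marrow. Aspirate flow is scheduled in section 3.4, and nothing in section 10.4.3 prevents its use for the 26. This stands: a reader might infer that the trial will certainly score the two groups differently, and the documents do not establish that. They leave it open.

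Two further limits also stand. The rule that suspicious flow is negative comes from the phase 1 account; that it governed all 64, who include phase 3 patients, is an inference. The suspicious-is-positive sentence sits in the peripheral-blood bullet, while 30/64 rests on marrow flow. And the documents are silent on whether the 64 had a count waiver.

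A reader might also infer a large assay effect from the share of CRs that were MRD-negative: 27/33 = 82% by IHC in phase 3, against 11 of about 21 CRs (64% of 33), or 52%, by three tests in phase 1. That contrast crosses trials with different doses and CR rates. On the scale actually tested the figures agree: 27/80 = 34% and 11/32 = 34%. Applying the 82% share to the 64% CR rate gives about 52% MRD-free CR, and an error of only about 4%.

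The reply does not remove the need to act. Nothing in the plan commits the analyst to aspirate flow, and even if it is used, sections 1.2.1 and 6.4.2 give opposite rules for suspicious results.

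**Conclusion.** The concern holds as a mismatch between the written MRD rules and the historical assay, together with a tested endpoint that is not pinned to one assay. The result turns on a single participant at 19/26. Under assumed reclassification of 5% to 15% of MRD-free CRs, power falls from 79.8% to between 66% and 36%. Under assumed upward shifts to 55% or 60%, one-sided error rises from 1.5% to 7% or 15%, and 24% is the upper bound. These are sensitivity figures, not estimates of the actual bias.

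A reader might go further and infer that the comparison favours the combination, or that no result from it could be read. The documents support neither: the four differences work in opposite directions, their sizes are unknown, and section 10.4.3 also reports the rates descriptively. Nor is this the plan's only formal test, since section 10.4.3 also has a p>0.30 check before the rituximab and Ruxience groups are pooled. The endpoint is secondary, and the primary safety endpoint is untouched.

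**What to change.** In sections 6.4.2 and 10.4.3:

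1. Define the tested endpoint once, as CR with MRD-negative marrow-aspirate flow, the test behind 30/64.
2. Reconcile sections 1.2.1 and 6.4.2 on suspicious results. Use in both groups the rule under which 30/64 was counted, or re-tabulate the 64 from existing NIH flow reports under the chosen rule.
3. Keep PCR exploratory.
4. Check whether the 64 had the blood-count waiver, and apply the same count criterion to both groups.
5. Report the alternative rule for suspicious results, and the IHC/blood definition, as sensitivity analyses.

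The cost is a wording change and modest re-tabulation, provided the historical reports are retrievable. The historical count may shift slightly, and the cut-off with it. No new sampling is needed, because aspirate flow is already scheduled at baseline, end of treatment, six months later and restaging.
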